### **10.2.4 Start Date**

The start date of the AE is the date that the first signs/symptoms were noted by the subject and/or investigator.

### **10.2.5 Stop Date**

The stop date of the AE is the date at which the subject recovered, the event resolved but with sequelae or the subject died.

### **10.2.6 Frequency**

Episodic AEs (eg, headache) or those which occur repeatedly over a period of consecutive days are intermittent. All other events are continuous.

### **10.2.7 Action Concerning Trial Drug**

- Drug withdrawn: a trial medication is stopped because of the particular AE.
- Dose not changed: the particular AE did not require stopping a trial medication.
- Unknown: only to be used if it has not been possible to determine what action has been taken.
- Not applicable: a trial medication was stopped for a reason other than the particular AE, for example, the trial has been terminated, the subject died, dosing with trial medication was already stopped before the onset of the AE.

### **10.2.8 Outcome**

- Recovered/resolved: subject returned to first assessment status with respect to the AE.
- Recovering/resolving: the intensity is lowered by one or more stages; the diagnosis has or signs/symptoms have almost disappeared; the abnormal laboratory value improved, but has not returned to the normal range or to the baseline value; the subject died from a cause other than the particular AE with the condition remaining “recovering/resolving.”
- Not recovered/not resolved: there is no change in the diagnosis, signs or symptoms; the intensity of the diagnosis, signs/symptoms, or laboratory value on the last day of the observed trial period has become worse than when it started; is an irreversible congenital anomaly; the subject died from another cause with the particular AE state remaining “Not recovered/not resolved.”

- Resolved with sequelae: the subject recovered from an acute AE but was left with permanent/significant impairment (eg, recovered from a cardiovascular accident but with some persisting paresis).
- Fatal: an AE that is considered as the cause of death.
- Unknown: the course of the AE cannot be followed up because of hospital change or residence change at the end of the subject's participation in the trial.

## **10.2.9 Collection and Reporting of AEs, SAEs, Special Interest AEs, and Abnormal LFTs**

### *10.2.9.1 Collection Period*

Collection of AEs (ie, AEs, SAEs, special interest AEs, and abnormal LFTs) will commence at the time the subject signs the informed consent. Routine collection of AEs will continue until the Follow-up Visit 10 to 14 days after the last dose of TAK-906. For subjects who discontinue prior to the administration of trial medication, AEs will be followed until the subject discontinues trial participation.

### *10.2.9.2 Reporting AEs*

At each trial visit, the investigator will assess whether any subjective AEs have occurred. A neutral question, such as "How have you been feeling since your last visit?" may be asked. Subjects may report AEs occurring at any other time during the trial. Subjects experiencing an SAE prior to the first exposure to investigational product must be monitored until the symptoms subside and any clinically relevant changes in laboratory values have returned to Baseline or there is a satisfactory explanation for the change. Nonserious AEs that begin prior to the first exposure to investigational product, related or unrelated to the trial procedure, need not be followed-up for the purposes of the protocol.

All subjects experiencing AEs, whether considered associated with the use of the trial medication or not, must be monitored until the symptoms subside and any clinically relevant changes in laboratory values have returned to Baseline or until there is a satisfactory explanation for the changes observed. All AEs will be documented in the AE page of the eCRF, whether or not the investigator concludes that the event is related to the drug treatment. The following information will be documented for each event:

- Event term.
- Start and stop date and time.
- Severity.
- Investigator's opinion of the causal relationship between the event and administration of trial medication(s) (related or not related).
- Investigator's opinion of the causal relationship to trial procedure(s), including the details of the suspected procedure.

- Action concerning trial medication.
- Outcome of event.
- Seriousness.

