### **7.4 Diet, Fluid, Activity**

#### **7.4.1 Diet and Fluid**

Subjects must abstain from all food and drink (except water) at least 8 hours before any clinical laboratory evaluations. In addition, both doses of TAK-906 will be administered after an overnight fast of at least 8 hours as food reduces its bioavailability by approximately 40%.

The bioavailability of itraconazole when administered as a PO solution is increased under fasted compared with fed conditions; therefore, itraconazole will be administered as fasted on Day 4 of

Period 2. A moderate-fat breakfast or snack may be administered on itraconazole-only days to alleviate gastrointestinal irritation. Itraconazole will be administered to subjects under clinic supervision on an outpatient basis on the morning of Days 1 to 3 of Period 2.

During confinement (optional), lunch will be provided approximately 4 hours after TAK-906 maleate dosing or 5 hours after itraconazole dosing, as applicable, on all days. Dinner will be provided approximately 9 or 10 hours after TAK-906 maleate or itraconazole dosing, respectively, on all days. An evening snack will also be permitted. The caloric content and composition of meals will be the same in each trial period. After the 24-hour postdose (Day 2 of Trial Period 1 and Day 5 of Trial Period 2) procedures have been completed, subsequent meals and snacks will be unrestricted in caloric content, composition, and timing.

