#### **9.4 Trial Drug Administration**

Eligible subjects will be allocated to trial treatment by nonrandom assignment on Period 1 Day 1 to receive PO TAK-906 maleate 25 mg capsule QD on Period 1 Day 1 and on Period 2 Day 4 at approximately the same time (between 0600 and 0900).

In Period 2, subjects will receive PO itraconazole 200 mg solution QD on Days 1 to 5 at approximately the same time (between 0600 and 0900). Itraconazole will be administered to subjects under supervision on an outpatient basis on the morning of Days 1 to 3 of Period 2. On Day 4, TAK-906 maleate will be administered 1 hour after itraconazole.

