#### **9.5 Confinement**

Period 1:

Subjects will report to the CRU the evening before the scheduled day of administration (Day -1) of the trial drug at the discretion of the investigator. Subjects will remain in the unit until after the PK sample collection at 48 hours after TAK-906 maleate dosing (the morning of Day 3). At the discretion of the investigator, subjects may be requested to remain in the CRU longer.

Period 2:

Subjects will report to the CRU the evening of Day 3 before the scheduled day of administration of the trial drug on Day 4 and at the discretion of the investigator. Subjects will remain in the unit until after the PK sample collection at 48 hours after TAK-906 maleate dosing (the morning of Day 6). At the discretion of the investigator, subjects may be requested to remain in the CRU longer.

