### **10.2.2 Assigning Causality of AEs**

The relationship of each AE to trial medication(s) will be assessed using the following categories:

Related: An AE that follows a reasonable temporal sequence from administration of a drug (including the course after withdrawal of the drug), or for which possible involvement of the drug can be argued, although factors other than the drug, such as underlying diseases, complications, concomitant drugs and concurrent treatments, may also be responsible.  
Not Related: An AE that does not follow a reasonable temporal sequence from administration of a drug and/or that can reasonably be explained by other factors, such as underlying diseases, complications, concomitant drugs and concurrent treatments.

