#### **11.1.4 Safety Analysis**

The safety set will be used for all summaries of safety parameters. These summaries will be presented by regimen (TAK-906 maleate alone, itraconazole alone, and TAK-906 maleate with itraconazole).

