#### 7.11.1 Adverse Events

A treatment-emergent adverse event (TEAE) will be defined as an AE or serious adverse event (SAE) that started or worsened after first study drug administration and within 30 days of last dose of study drug (onset date – date of last dose + 1  $\leq$  30). All AE verbatim terms will be coded by system organ class (SOC) and preferred term (PT) using the MedDRA dictionary.

TEAEs will be summarized by overall and the following categories: Period 1 (onset on and after TAK-906 dosing on Period 1 Day 1 and before the dosing of itraconazole on Period 2 Day 1), Period 2 Day 1 post-dose to Day 4 pre-dose (after itraconazole dosing on Period 2 Day 1 and before TAK-906 dosing on Period 2 Day 4), and Period 2 Day 4 post-dose and thereafter (after TAK-906 and itraconazole dosing on Period 2 Day 4). The tables will include the number and percentage (N [%]) of subjects reporting any event for that term. The following is a list of TEAE summary tables to be generated.

- Overview of TEAEs (at both subject and event level).
- TEAEs by SOC and PT (at both subject and event level).
- Subject Mappings for TEAEs.
- TEAEs by PT.
- Relationship of TEAEs to Study Drug by SOC and PT.
- Drug-Related TEAEs by SOC and PT.
- Intensity of TEAEs by SOC and PT.
- Intensity of Drug-Related TEAEs by SOC and PT.

For each category and overall, subjects reporting more than 1 occurrence for a term (SOC or PT) being summarized will be counted only once using the most extreme incident (most severe for the intensity tables and related for the relationship to study drug tables).

Data listings will be provided for all TEAEs, PTEs, TEAEs that led to study drug discontinuation, TEAEs that led to abnormal liver functions, SAEs, AEs that resulted in death, and AEs occurring more than 30 days after the last dose of study medication.

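### From the TAK-906 dose on Period 2 Day 4, the planned relatedness tables cannot show whether TAK-906 or itraconazole was suspected

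*Protocol*

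**What the plan says.** Protocol 10.2.2 sets one two-level scale: "The relationship of each AE to trial medication(s) will be assessed using the following categories", namely related or not related. Related applies when involvement of the drug can be argued, even if other factors may also be responsible. Not related applies when the event lacks a reasonable time sequence and/or "can reasonably be explained by other factors, such as underlying diseases, complications, concomitant drugs and concurrent treatments". Nothing tells the investigator to judge the two drugs separately.

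Protocol 10.2.9.2 lists what is documented per event. The drug item is the opinion on the "causal relationship between the event and administration of trial medication(s) (related or not related"). The next item, on trial procedures, does ask for details of the suspected procedure.

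Protocol 11.1.4 plans three safety columns: "These summaries will be presented by regimen (TAK-906 maleate alone, itraconazole alone, and TAK-906 maleate with itraconazole"). SAP 7.11.1 implements these as onset categories:

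- Period 1, up to the first itraconazole dose.
- After itraconazole on Period 2 Day 1, until TAK-906 on Day 4.
- After both drugs on Day 4, and thereafter.

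The SAP's relatedness outputs are "Relationship of TEAEs to Study Drug by SOC and PT", a drug-related table, and an intensity table for drug-related events. A subject with several occurrences of a term counts once, as related if any occurrence was related.

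**The concern.** The secondary objective is the safety and tolerability of a single TAK-906 dose in the presence and absence of the inhibitor. In Period 1, a drug-related event can reflect only TAK-906. From Day 4 it can reflect either drug. A reader comparing the two columns could take itraconazole's own effects for poorer tolerability of TAK-906 when its exposure is raised.

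The possibility is not remote. The protocol foresees gastrointestinal effects of itraconazole in its diet rules: "A moderate-fat breakfast or snack may be administered on itraconazole-only days to alleviate gastrointestinal irritation". TAK-906 is intended for gastroparesis, so gastrointestinal events are likely to be read with interest. With about 12 subjects, one reclassified subject moves a column by 1/12 = 8.3 percentage points.

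**Working it through.** The plan states no figure for drug-related events, so there is nothing to reproduce. The check is a comparison of texts, followed by two small calculations.

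**1. Is itraconazole a study drug?** Neither document defines trial drug, trial medication or study drug.

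- For: Protocol 9.4, headed Trial Drug Administration, covers both drugs ("In Period 2, subjects will receive PO itraconazole 200 mg solution QD on Days 1 to 5"). Section 8.1, Clinical Trial Drug, covers the supply of itraconazole. Sections 10.2.2 and 10.2.9.2 allow for a plural, and 10.2.7 refers to a trial medication. Section 11.1.4 has an itraconazole-alone safety regimen.
- Against: Protocol 9.5 has subjects report on "the evening of Day 3 before the scheduled day of administration of the trial drug on Day 4". This fits TAK-906 only, since itraconazole starts on Day 1.

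Inclusion is the better reading, but it is not settled.

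**2. Where does an itraconazole-caused event go?**

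| Onset | SAP category | If study drug includes itraconazole | If study drug is TAK-906 only |
|---|---|---|---|
| Before the first itraconazole dose | Period 1 | Cannot occur | Cannot occur |
| From itraconazole on Period 2 Day 1 until TAK-906 on Day 4 | Itraconazole alone | Related, but in its own column | May be rated not related, as due to a concomitant drug |
| After TAK-906 on Day 4, including after the Day 5 itraconazole dose | Combination | Related, and indistinguishable from a TAK-906 event | Related or not related can each be defended |

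Only the last row is a problem. Under either reading, the table there does not show which drug was suspected.

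**3. The Day 5 dose.** Itraconazole is given at the same time each day, and TAK-906 follows it by 1 hour on Day 4. The Day 5 itraconazole dose therefore falls 24 − 1 = 23 hours after TAK-906. At the stated fasted half-life of about 4 hours (Protocol 4.1), that is 23 / 4 = 5.75 half-lives. Inhibition could lengthen the half-life, by an amount not known in advance. An event after this dose could still be mainly itraconazole's, yet it falls in the combination category.

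**4. Does the itraconazole-alone category serve as a control?** Only partly.

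- Food: breakfast or a snack is allowed on itraconazole-only days, while the Day 4 dose is taken fasted. Protocol 7.4.1 says the bioavailability of the solution is higher when fasted.
- Length: the category runs from the Day 1 dose to TAK-906 on Day 4, about 3 × 24 + 1 = 73 hours. The combination category runs on to a follow-up visit 10 to 14 days after TAK-906.

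**5. Illustrative size.** The documents give no itraconazole event rate. Assume that 5% to 20% of subjects have an event due to itraconazole alone from Day 4 onward that is rated related:

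- 12 × 0.05 = 0.6 subjects
- 12 × 0.20 = 2.4 subjects

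These would be added to drug-related in the combination column and none in Period 1, with no effect of TAK-906 at all.

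**The case against.** The strongest reply is that the plan already isolates itraconazole. Events from Period 2 Day 1 until TAK-906 on Day 4 have their own column, in the same subjects. All-cause incidence across the three columns addresses the secondary objective descriptively without relying on causality judgements. Event times and dose times are recorded, so each event can be placed against each dose. A higher related rate under a two-drug regimen is not wrong, because the column describes the regimen. Per-drug attribution would also be soft: the trial is open-label, and the threshold for related is low enough that both drugs could often be marked.

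Much of this stands. It is why all-cause counts should stay the main comparison. It does not supply the investigator's opinion on which drug was suspected. Dose timing alone cannot recover that opinion when the drugs are given 1 hour apart.

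Three stronger readings might be inferred, and the documents support none of them:

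- That itraconazole events throughout Period 2 land in the combination column. Those starting before TAK-906 on Day 4 do not.
- That such events must be entered as related. This depends on the undefined term, and the not-related category admits concomitant drugs as an explanation.
- That the data will hold no per-drug attribution. The eCRF is not among the documents, the plural wording does not rule out separate fields, and the SAE form asks for the name of the trial medication(s). Even with separate fields, however, the SAP plans no table that would use them.

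**Conclusion.** The point holds for events starting after TAK-906 on Period 2 Day 4. For these, neither document requires causality per drug, and no planned table separates the drugs. If itraconazole is a study drug, the drug-related comparison between Period 1 and the combination is confounded by itraconazole's own effects. If it is not, the rating of such an event is left to interpretation.

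The effect is confined to the relationship table, the drug-related table, the intensity table for drug-related events, and the drug-related counts in any overview. All-cause counts do not change with how causality is recorded. The pharmacokinetic primary objective is untouched. The figure of 0.6 to 2.4 subjects shows scale under an assumed rate and should not be read as a forecast. This is a worthwhile, inexpensive improvement to what is collected and tabulated, not an error that invalidates the safety analysis.

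**What to change.** - **Definition.** State in the protocol and SAP that study drug (trial drug, trial medication) means TAK-906 and itraconazole.
- **Protocol 10.2.2 and 10.2.9.2.** Record two related/not-related answers per event, one for each drug. Both may be related.
- **SAP 7.11.1.** Present the relatedness tables as related to TAK-906, related to itraconazole, and related to either, within the three existing onset categories.
- **Interpretation.** Keep all-cause events by onset category as the main descriptive comparison. Treat related to TAK-906 as supportive, because attribution during open-label co-administration is partly judgement.

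The cost is one extra field on the adverse event page and a few table columns. The either category preserves the combined result, so nothing is lost. The field should be in place before event data are collected, since the investigator's opinion at the time is hard to reconstruct later. The definition has one side effect: the Day 5 itraconazole dose becomes the last dose of study drug, so the SAP's windows counted from last dose (30 days for events, 7 days for markedly abnormal values) should be checked against it.

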#### *10.2.9.3 Reporting SAEs*

When an SAE occurs through the AE collection period it should be reported according to the procedure outlined below:

A Takeda SAE form must be completed, in English and signed by the investigator immediately or within 24 hours of first onset or notification of the event. The information should be completed as fully as possible but contain, at a minimum:

- A short description of the event and the reason why the event is categorized as serious.
- Subject identification number.
- Investigator's name.
- Name of the trial medication(s).
- Causality assessment.

The SAE form should be transmitted within 24 hours to the attention of the contact listed in Section 14.1.1.

Any SAE spontaneously reported to the investigator after the AE collection period should be reported to the sponsor if considered related to trial participation.

Reporting of SAEs that begin before the first administration of investigational product will follow the same procedure for SAEs occurring on treatment.

#### SAE Follow-Up

If information is not available at the time of the first report becomes available at a later date, the investigator should complete a follow-up SAE form or provide other written documentation and fax it immediately within 24 hours of receipt. Copies of any relevant data from the hospital notes (eg, ECGs, laboratory tests, discharge summary, postmortem results) should be sent to the addressee, if requested.

All SAEs should be followed up until resolution or permanent outcome of the event. The timelines and procedure for follow-up reports are the same as those for the initial report.

#### *10.2.9.4 Reporting of Abnormal LFTs*

If a subject is noted to have ALT or AST elevated  $>3\times$ ULN on 2 consecutive occasions, the abnormality should be recorded as an AE. In addition, an LFT Increases eCRF must be completed providing additional information on relevant recent history, risk factors, clinical signs and symptoms, and results of any additional diagnostic tests performed.

If a subject is noted to have ALT or AST  $>3\times$ ULN and total bilirubin  $>2\times$ ULN for which an alternative etiology has not been identified, the event should be recorded as an SAE and reported as per Section 10.2.9.3. The investigator must contact the Medical Monitor for discussion of the relevant subject details and possible alternative etiologies, such as acute viral hepatitis A or B or other acute liver disease. Follow-up laboratory tests as described in Section 9.2 must also be performed. In addition, an LFT Increases eCRF must be completed and transmitted with the Takeda SAE form (as per Section 10.2.10).

#### **10.2.10 Safety Reporting to Investigators, IRBs or IECs, and Regulatory Authorities**

The sponsor will be responsible for reporting all suspected unexpected serious adverse reactions (SUSARs) and any other applicable SAEs to regulatory authorities, investigators and IRBs or independent ethics committees (IECs), as applicable, in accordance with national regulations in the countries where the trial is conducted. Relative to the first awareness of the event by/or further provision to the sponsor or sponsor's designee, SUSARs will be submitted within 7 days for fatal and life-threatening events and 15 days for other serious events, unless otherwise required by national regulations. The sponsor will also prepare an expedited report for other safety issues where these might materially alter the current benefit-risk assessment of an investigational medicinal product or that would be sufficient to consider changes in the investigational medicinal products administration or in the overall conduct of the trial. The investigational site also will forward a copy of all expedited reports to his or her IRB or IEC in accordance with national regulations.

## **11.0 STATISTICAL METHODS**

### **11.1 Statistical and Analytical Plans**

A statistical analysis plan (SAP) will be prepared and finalized before database lock. This document will provide further details regarding the definition of analysis variables and analysis methodology to address all trial objectives.

A targeted data review will be conducted before database lock. This review will assess the accuracy and completeness of the trial database, subject evaluability, or appropriateness of the planned statistical methods.

#### **11.1.1 Analysis Sets**

##### *11.1.1.1 Safety Set*

The safety set will consist of all subjects who are enrolled and receive at least 1 dose of trial drug. Subjects in this analysis set will be used for demographic, baseline characteristics, and safety summaries.

